7.2 Statistical Evaluation of Primary Endpoint

Statistical Analysis of Primary Clinical Efficacy Outcome

The primary clinical efficacy endpoint will be calculated as the proportion of subjects with a 180 day mRS of 0 to 3. Subjects who die prior to the 180 day mRS assessment will be included in the analysis with an mRS score of 6. The proportion of patients with favorable clinical outcomes based on this criterian will be calculated, and a 95% confidence interval will be presented. The number and percentage of subjects in each mRS category (0 to 6) will also be presented.

Statistical Analysis of Primary Technical Efficacy Outcome

The proportion of subjects experiencing surgical success based on the following criteria will be calculated, and a 95% confidence interval will be presented.

- Predominantly or Only ICH: Reduction to < 15 cc total volume AND >60% reduction in hemorrhage volume on immediate post-treatment CT scan
- $\circ~$ Predominantly or Only IVH: mGraeb score of < 5 on day 7 CT scan

7.3 Missing Data and Imputation Methods

Under the ITT principle, all patients who are enrolled are included in the analysis. Therefore, missing data, especially in the outcome measures, can be problematic. Every effort is to be made to keep all missing data, particularly the Day 180 outcomes, to a minimum. Despite the clinical sites' best efforts, some missing data may be inevitable mainly due to lost-to-follow-up (LTFU). The number and proportion of subjects eligible for and compliant with each follow-up examination will be presented. Subjects who withdraw from the study will be tabulated with reasons for withdrawal. Since the primary endpoint is defined using mRS, subjects deceased during study follow-up will be scored as mRS 6. Other subjects not completing the 180-day follow-up visit will be categorized for the primary endpoint using the mRS as of the last available follow-up visit or discharge (whichever is later). As a sensitivity analysis, we will also perform analysis after excluding subjects without 180-day follow-up evaluations. Additional details will be provided in the Statistical Analysis Plan (SAP).

7.4 Secondary Statistical Analysis

7.4.1 Secondary Endpoints

The secondary effectiveness variables:

- mRS at 30 and 90 days The number and percentage of subjects who experience mRS 0 to 3 will be calculated along with the 95% confidence interval. Frequency counts and percentage of subjects within each category will be provided.
- Length of hospital stay The median total length of stay and median ICU length of stay along with the interquartile range will be provided.
- Requirement for VPS The number and percentage of subjects who have VPS placement will be calculated along with the 95% confidence interval.

7.5 Safety Analysis

7.5.1 Safety Outcomes

Several specific adverse events are monitored throughout the study. However the primary safety outcome to be assessed at completion of the trial will be death within 30 days.

The proportion of deaths for any reason through 30 days will be calculated and a 95% confidence interval will be presented. Survival estimates will be generated to evaluate the time-to-death using the Kaplan-Meier methodology for all deaths through 30 days.

All adverse events will be summarized by showing the number and percent of patients which report the event. Events will also be reported by relationship to the procedure or device.

7.5.2 Interim Safety Monitoring

7.5.2.1 Stopping the Trial Based on Interim Safety Data

The EOC and DSMB will receive periodic safety reports of all AEs and SAEs. In addition, the following specific endpoints will be assessed by the medical monitor and presented:

- Death (all cause) within 30 days of enrollment
- Death within 7 days of enrollment: Immediate peri-procedural death
- Symptomatic Re-Hemorrhage or New Hemorrhagic Event: any new intracranial hemorrhage or increase in size of pre-existing hemorrhage (IPH, IVH or extra-axial bleed) within 30 days associated with an increase of 4 or more points on the NIHSS or GCS increase ≥ 2 persisting for at least 24 hours, and/or requiring emergency surgical decompression or resulting in death.
- Symptomatic Evolution of Peri-hematomal Edema: Edema with increased mass effect or uncontrolled ICPs within 30 days requiring emergency surgical decompression NOT related to new or increased hemorrhage (i.e. edema related) associated with an increase of 4 or more pointon the NIHSS or GCS increase >2 persisting for at least 24 hours and/or requiring emergency surgical decompression or resulting in death.
- Symptomatic Ischemic Stroke: A new ischemic stroke (ipsilateral, contralateral; contiguous with bleed/operative site or remote; cortical, subcortical or perforator distribution) within 30 days associated with an increase of 4 or more points on the NIHSS or GCS increase ≥2 persisting for at least 24 hours and/or requiring emergency surgical decompression or resulting in death.
- Surgical complications related to Apollo / Artemis MIES: Surgical site infection, brain abscess or confirmed meningitis, or documented complication(s) deemed specifically related to the procedural anesthetic (medication, access or intubation related) within 30 days.

Additional details of the monitoring plan will be included in the study SOP and DSMB charter.

7.6 Blinding

This single-arm treatment registry is not blinded. Blinding the study is not required for interpretation of outcomes.

8. Study Withdrawal

Subjects may be terminated or withdrawn from the study for the following reasons:

- Voluntary withdrawal of consent— meaning that a subject voluntarily chooses not to participate further in the study. All data collected up to the withdrawal of consent will be maintained in the study database.
- Lost to follow-up defined as a subject who is more than one month late to a study visit and for whom 5 documented telephone attempts to contact the subject and at least one certified letter were unsuccessful.
- Subjects may also be withdrawn at the investigator's discretion if within their best interest.

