4.4 Study Visits

Subjects enrolled to this study will follow the below visits schedule according to standard of care for stroke patient follow-up.

- Pre-Treatment
- Procedure
- Post procedure (24 hours, Apollo / Artemis MIES patients)
- 7 days post-enrollment or Discharge (whichever comes first)
- 1 month follow-up (+/- 14 days)
- 3 month follow-up (+/- 21 days)
- 6 month follow-up (+/- 28 days)

4.5 *Recruitment*

The target population for the INVEST registry are adult patients who have a diagnosis of supratentorial intracranial hemorrhage who do not require emergent open surgical decompression related to uncontrolled intracranial pressure or mass effect, who do not qualify for the INVEST multi-center Feasibility and who are to be treated with Apollo or Artemis MIES at an INVEST center.

Potential study participants and/or their legal authorized representative will be identified by the study team at each site to obtain consent and determine eligibility. Up to 30 United States sites will be included in this study and enroll up to 50 patients.

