5.8 Follow-Up Examination

5.8.1 Clinical

Several clinical outcome measures were selected for this study. These were chosen on the basis of their reliability, familiarity to the neurologic community, adaptability for use in patients who have had a stroke, and comparability to end points used in other trials of intracranial hemorrhage. All scores will be recorded in source documentation and entered into the electronic case report forms.

- 1. modified Rankin Scale (mRS, Appendix 4): mRS is an overall assessment of global handicap. In the original Rankin Scale, a score of zero indicates the absence of symptoms and a score of 5, severe disability. The modified Rankin Scale adds a score of 6 for fatal outcomes. A historical mRS will be obtained to assess the patient's level of function prior to the ICH. The score will be repeated as specified in Table 1.
- 2. The National Institutes of Health Stroke Scale (NIHSS, Appendix 5) is a 42-point scale that quantifies neurologic deficits in 11 categories. Normal function without neurologic deficit is given a score of zero. NIHSS should be done by a certified examiner as close to the specified times as possible.
- 3. EQ-5D-5L (Appendix 6) is a standardized instrument for use as a measure of health outcome. Applicable to a wide range of health conditions and treatments, the questionnaire provides a simple descriptive profile and a single index value for health status.

All day 7, discharge, day 30, day 90 and day 180 clinical outcome measures will be assessed by a qualified member of the research or clinical team either in person at a clinic visit, by phone or by mailed questionnaire. The schedule of neurological assessments is listed in Table 1. At each visit, the patient's medical record will be surveyed for any new or interim neurological adverse or serious adverse events. In addition, the patient or LAR will be asked about any interim neurological adverse or serious adverse events. The subject or LAR will also be specifically asked about any interim neurosurgical procedures.

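### Section 8 permits a subject who cannot be reached at the 1- or 3-month visit to be terminated before the 180-day window opens, and no 180-day mRS attempt is then required

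*Combined protocol and SAP*

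**What the plan says.** Section 8 (Study Withdrawal) introduces its list with "Subjects may be terminated or withdrawn from the study for the following reasons". Three reasons follow: withdrawal of consent, loss to follow-up, and the investigator's judgment.

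- **Loss to follow-up** has two conditions, and both must hold. The first is lateness: "Lost to follow-up defined as a subject who is more than one month late to a study visit". The second is failed contact: "5 documented telephone attempts to contact the subject and at least one certified letter were unsuccessful". No particular visit is named.
- **Investigator withdrawal**: "Subjects may also be withdrawn at the investigator's discretion if within their best interest". Nothing is said about outcome collection afterwards.

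Other sections bear on this:

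- Section 4.4 sets visits at 1, 3 and 6 months, with windows of 14, 21 and 28 days either side.
- Section 5.8.1 lets outcomes be assessed "either in person at a clinic visit, by phone or by mailed questionnaire". At each visit the site also reviews the medical record and asks the subject or the legally authorized representative (LAR) about events.
- Section 7.3 says "Every effort is to be made to keep all missing data, particularly the Day 180 outcomes, to a minimum". It scores deaths as mRS 6 and gives other subjects without a 180-day visit their latest earlier mRS. A sensitivity analysis leaves those subjects out.
- Section 8.1 asks the site to find out why a visit was missed.
- Section 15 describes records of contact attempts up to the point where participation finishes or is terminated.
- Section 16.2 ends SAE recording at the 180-day visit, death or consent withdrawal.

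**The concern.** The primary clinical endpoint is mRS 0 to 3 at 180 days. A loss-to-follow-up rule that can operate at an interim visit may close a subject's participation before that outcome is due. A person who cannot be reached in the second or fourth month may be reachable in the sixth, and phone or mail would be enough.

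If the site stops at termination, 7.3 fills in an old score. For a subject lost at the 1-month visit this is the discharge or day-7 mRS; for one lost at the 3-month visit it is normally the 1-month mRS. A later death that nobody learns of would not be scored 6. The sensitivity analysis and the per-protocol sample (6.1.1) drop these subjects, so neither recovers the outcome. The SAP to which 7.3 defers further detail cannot recover it either, because the data were never sought.

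**Working it through.** **The plan's own attrition figure.** Section 7.1 takes 200 enrolled and 10% attrition: 200 × (1 − 0.10) = 180. With 61/180 = 33.9%, the half-width is 1.96 × √(0.339 × 0.661 / 180) = 6.9 points, giving 27.0% to 40.8%. The plan's 27% to 41% is reproduced. The 10% covers attrition from every cause, so it does not measure the effect of section 8.

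**When the lateness condition can be met.** Inputs are the visit days and windows in 4.4, with 1, 3 and 6 months taken as days 30, 90 and 180. One month is taken as 31 days, the reading least favorable to the concern. Section 8 does not say whether lateness runs from the target day or from the close of the window, so both are shown.

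| Missed visit | From target day | From window close |
|---|---|---|
| 1 month | 30 + 31 = day 61 | 30 + 14 + 31 = day 75 |
| 3 months | 90 + 31 = day 121 | 90 + 21 + 31 = day 142 |

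The 6-month window runs from 180 − 28 = day 152 to 180 + 28 = day 208. The lateness condition can therefore be met before it opens by:

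- 1-month visit: 152 − 61 = 91 days, or 152 − 75 = 77 days
- 3-month visit: 152 − 121 = 31 days, or 152 − 142 = 10 days

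A 28-day month moves each date 3 days earlier and widens each gap by 3 days. These are the earliest dates for lateness alone; the calls and the letter must also have failed.

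**What follows termination.** Section 15 describes contact records only up to completion or termination. Section 8.1 concerns the reason for a missed visit. No section requires a 180-day mRS attempt in a terminated subject. Section 16.2 keeps SAE recording open to the 180-day visit, death or consent withdrawal; loss to follow-up and investigator withdrawal are not on that list. The two sections therefore give different end points for the same subject.

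**Size per subject.** At the cap of 50 (section 4.5), 1/50 = 2 points on the primary proportion. At the 200 in section 7.1, 1/200 = 0.5 points. The conflict between 50 and 200 is a separate matter.

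**The case against.** The strongest reply is that the rule is narrow. It says subjects may be terminated, and it acts only after more than a month's delay, five failed calls and a failed letter. A reader might infer that a missed visit by itself ends follow-up; the text does not say that. This limits how often the rule would apply, but it does not make the rule safe at an interim visit.

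Three further inferences go beyond the documents:

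- **That the missing outcomes are probably related to prognosis, because 8.1 mentions re-hospitalization.** In that example the site has learned why the visit was missed, so the subject has been reached and does not meet the definition of loss. The documents give no evidence on the prognosis of those who cannot be reached.
- **That about 5 of 50 outcomes are at stake.** That carries all-cause attrition, stated for 200 subjects, over to the cap of 50. The documents do not say how many would be terminated early, reachable at day 180, or in a different mRS category by then.
- **That the best-interest clause can only remove data and should be deleted.** Follow-up includes examinations and scales from which a subject may reasonably be spared. The gap is that nothing provides for remote follow-up afterwards.

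It can also be said that 16.2 and 5.8.3 keep SAEs, including deaths, under record to 180 days, and that the last column of Table 1 covers the end of study as well as 6 months. Both points have weight. The SAE text means that section 8 cannot be read as plainly ending all data collection, but it does not call for an mRS. The Table 1 label could support an exit assessment in a subject who is still in contact; it does not help with one who is not.

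Finally, 7.3 tabulates visit compliance and withdrawal reasons and adds a sensitivity analysis, and the registry tests no hypothesis. That lowers the stakes. The merits of carrying an earlier score forward belong to 7.3 and are not counted again here.

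**Conclusion.** The point holds as a defect in a follow-up rule. Under section 8 a subject unreachable at the 1- or 3-month visit may be terminated at least 10 days before the primary window opens. No section then requires a 180-day mRS attempt. The rule works against the aim stated in 7.3 and needs to be reconciled with 16.2.

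The timing rests on 30-day visit spacing and a month of at most 31 days; it holds whether lateness runs from the target day or from window close. The number of subjects affected cannot be derived. Each is worth 2 points at the 50-patient cap, and only if the substituted score falls on the other side of the mRS 3 boundary from the true one. Early termination is possible, not automatic, and no direction of bias can be claimed. The repair is cheap and worth making.

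**What to change.** Change section 8 as follows:

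1. Treat a 1- or 3-month visit at which the subject cannot be reached as a missed visit, with the subject remaining in the study.
2. Declare loss to follow-up only when the 6-month window has closed without contact, keeping the existing call and letter requirements.
3. Attempt the 180-day mRS and vital status in every enrolled subject who has not withdrawn consent, by clinic, phone or mail, through the LAR, or by record review. Section 5.8.1 already provides for these routes.
4. Keep the best-interest clause, but state that it ends in-person study assessments while remote or record follow-up to day 180 continues unless consent is withdrawn.

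Align sections 15 and 16.2 so that contact attempts and SAE recording end at the same points. The cost is protocol wording and one more round of contact per affected subject, by methods already allowed.

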8.1 Unattended Visits

Any study subject who does not attend a scheduled follow-up visit should be contacted by site personnel to determine the reason for the missed appointment(s). If the missed visit was due to a serious adverse event, (e.g., re-hospitalization) an AE Case Report Form (CRF) must be completed and any reporting requirements met.

9. Data Safety Monitoring Board (DSMB)

A DSMB will be comprised of 4 members not participating in the trial and will include neurovascular specialist physicians and a statistician. The DSMB will exercise review of the overall safety of the trial, periodically review all adverse events occurring in the trial, and make recommendations to adjustments in the study protocol, should any be considered necessary for safety or other related reasons.

The TOC will consist of the study PIs, statistical PI, project managers, data managers, and others deemed necessary in overseeing the day-to-day operations of the trial. The TOC will review study progress, study conduct at individual clinical sites, other clinical site performance measures, and blinded DSMB reports.

11. Steering Committee (SC)

The steering Committee will be comprised of the trial PI's and selected principal investigators from participating centers. The SC will be responsible for overall supervision and execution of the trial including adherence to protocol, progress of enrollment, patient safety and consideration of new information. Daily trial management is the responsibility of the TOC. It will provide key input to the SC for study planning, execution and data presentation.

12. Study Management

As the study Principal Investigators, [name], [name], and [name], have overall responsibility for the conduct of the study according to 21 CFR 812, 21 CFR Part 50, Good Clinical Practice (GCP) Guidelines (Guidance for Industry, E6 Good Clinical Practice Consolidated Guidance, ICH, April 1996), ISO 14155: Part 1 and 2, the Declaration of Helsinki, Medical Device Directive, Annex X, FDA and all applicable regulatory requirements. For this study, the PIs will have certain direct responsibilities and will delegate other duties to appropriately qualified individuals. All personnel participating in the conduct of this clinical trial will be qualified by training, education, and experience to perform his or her respective tasks.

*NOTE: A complete list of participating investigators will be maintained and will be available upon request.

13. Investigator Responsibilities

The Investigator(s) shall be responsible for the day-to-day conduct of the investigation as well as for ensuring that the investigation is conducted according to all signed agreements, applicable elements of ISO 14155, the Clinical Investigational Plan, applicable FDA regulations, and the principles that have their origin in the Declaration of Helsinki.

The investigator is also responsible for having control of the device under investigation, for protecting the rights, safety and welfare of subject's under the investigator's care and for obtaining informed consent in accordance with 21 CFR Part 50. Each Investigator must sign the Investigator Agreement (or an equivalent and a Financial Disclosure) prior to becoming eligible to enroll subjects in this trial.

Responsibilities of the Investigator include, but are not limited to:

Ensuring that IRB approval is obtained prior to undertaking the trial at a clinical site; and, that participation of a subject in a clinical trial includes obtaining written informed consent prior to randomization, and/or other non-standard of care study-related assessments;

Providing the study TOC with accurate and complete financial information per 21 CFR Part 54; Ensuring that all personnel assisting with the clinical trial are adequately informed and understand their trial-related duties and functions;

It is recommended that each site identify a study coordinator for this study. Working with and under the authority of the clinical site Principal Investigator, the study coordinator assures that all study requirements are fulfilled, and is the contact person at the site for all aspects of study administration.

The Investigator will allow direct access to source data/documents for trial related monitoring, audit, IRB/EC review and regulatory inspection. Also, the investigator will allow auditing of their clinical investigational procedure(s).

14. Required Documents from the Investigator

- 1) At a minimum, the investigational site will provide the following documents to the TOC:
- 2) Signed Investigator Agreement,
- 3) Investigators Agreement
- 4) Written and dated IRB/EC approval,
- 5) Written and dated IRB/EC approval for ICF document,
- 6) IRB/EC approval for any other written documents to be provided to the study subject (e.g., advertising),
- 7) HIPAA documentation,
- 8) *Investigator and Co-Investigators' current Curriculum Vitae,
- 9) Current medical licenses,
- 10) Any other relevant documents requested by the TOC or the reviewing IRB/EC or other regulatory authorities,
- 11) FDA Form 3454 or 3455 (or equivalent) regarding financial interests
- 12) Fully executed contract.
- 13) Ongoing IRB approval documents
- 14) Source Documents for data verification
- 15) Site Delegation of Authority Log

A site may not begin study participation until all of the above listed documents have been provided to the study management team.

* With regard to the Sub-Investigators current CVs, the study may begin once the CV of the site PI, IRB approval and IRB approved consent and privacy statement, the investigator's agreement, Medical License, and financial disclosures, fully-executed contract, and others listed above, have been received. No additional Investigators may participate in the study, however, until a copy of their CV and all other required documents have been provided to the TOC.

15. Investigator Records

The Investigator must ensure that all study subject records are stored for at least 6 years after the end of the clinical study. To avoid error, the study site should contact [name] prior to the destruction of study records to ensure

that they no longer need to be retained. In addition, [name] should be contacted if the Investigator plans to leave the investigational site so that arrangements can be made for the handling or transfer of study records.

The Investigator will also maintain original source documents from which study-related data are derived, which include, but are not limited to:

Clinic progress notes recording subject's medical history and medications;

Medical charts with operative reports and condition of subject upon discharge;

Medical records regarding AEs/SAEs, including treatment and clinical outcome;

Results of diagnostic examinations, imaging (such as x-rays, MRIs), as well as the report of the radiologist's reading/interpretation of diagnostic imaging;

Signed notes of phone calls and/or correspondence indicating investigational site's attempts to follow study subjects at the required follow-up visits until subject's participation in the study is complete or terminated;

Records relating to patient death (e.g., death certificate, autopsy report, if available, or terminal medical records).

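### Section 7.3 scores a survivor who misses the 180-day visit on the last earlier mRS even when a recorded SAE came after it, and no stated analysis can count that deterioration as unfavorable

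*Combined protocol and SAP*

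**What the plan says.** Four parts of the protocol bear on this.

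- **8.1 (Unattended Visits).** A subject who misses a scheduled follow-up visit "should be contacted by site personnel to determine the reason for the missed appointment(s". For one particular cause it adds: "If the missed visit was due to a serious adverse event, (e.g., re-hospitalization) an AE Case Report Form (CRF) must be completed", along with any reporting that is due. It mentions neither an mRS at that contact nor a rescheduled assessment.
- **7.3 (Missing Data and Imputation Methods).** Deaths are handled separately: "subjects deceased during study follow-up will be scored as mRS 6". Everyone else without a completed 180-day visit "will be categorized for the primary endpoint using the mRS as of the last available follow-up visit or discharge (whichever is later". The one sensitivity analysis it names reads: "we will also perform analysis after excluding subjects without 180-day follow-up evaluations". It also gives a general instruction: "Every effort is to be made to keep all missing data, particularly the Day 180 outcomes, to a minimum".
- **5.8.1 (Clinical).** The clinical outcome measures, day 180 included, are to be assessed "either in person at a clinic visit, by phone or by mailed questionnaire".
- **6.1.1 (Definition of Analysis Samples).** The per-protocol sample leaves out subjects whose 180-day primary efficacy outcome is missing for a reason other than death.

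Section 7.2 defines the primary clinical result as the proportion with a 180-day mRS of 0 to 3.

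**The concern.** When an SAE is the reason for the missed visit, whether the outcome is observed may depend on the outcome itself. The score that 7.3 carries forward was taken before the event. Take a survivor with mRS 3 at day 90 who is later hospitalized with a disabling event and has no 180-day mRS. That subject counts as favorable, although the study's own adverse event record shows a later event. SAEs are recorded to the end of the 180-day follow-up (16.2), so the information is in the database but the primary analysis does not use it.

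The other stated analyses do not repair this. They remove the subject, so the subject is either favorable or absent.

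The wording of the 7.3 trigger adds an ambiguity. It turns on whether the visit was completed, not on whether an mRS exists. If a site obtains an mRS by phone while asking why the appointment was missed, the text does not say whether that value replaces the carried one.

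At stake is the primary clinical proportion of a registry whose data, according to the design rationale in section 2, may inform a later pivotal trial.

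**Working it through.** **1. The plan's own figure.** Section 7.1 assumes 61/180 favorable, with 200 enrolled and 10% attrition.

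- Rate: 61/180 = 33.9%.
- Half-width: 1.96 × √(0.339 × 0.661 / 180) = 6.9 points, so the interval is 27.0% to 40.8%. This matches the stated 27% to 41%.
- Attrition: 180 / (1 − 0.10) = 200, as stated.

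These figures reproduce, but none of them measures the effect of the carry-forward rule.

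**2. How each stated analysis treats the subject.** The subject is a survivor with last mRS 0-3, a later SAE, a true mRS above 3 and no 180-day mRS.

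| Analysis | Treatment | Result |
|---|---|---|
| Primary, ITT (7.3) | last mRS carried forward | favorable |
| Sensitivity (7.3) | excluded | absent |
| Per-protocol (6.1.1) | excluded | absent |

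SAEs are summarized in the safety analysis (7.5.1), but that does not change the mRS proportion.

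**3. Size per subject.** With k such subjects among N, the reported rate is too high by k/N.

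- N = 50 (the enrollment cap in the synopsis and 4.5): 1/50 = 2 points each.
- N = 200 (the figure in 7.1): 1/200 = 0.5 point each.

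**4. Illustration.** The documents do not give k. Assume 10% missing and a reported rate of 34%.

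- At N = 50, 10% is 5 subjects. If the 34% rate also applied to them, 5 × 0.34 = 1.7 would have a last mRS of 0-3, whatever the reason for the miss. Those with an SAE who also worsened beyond 3 are a subset. I therefore use k = 0 to 2.
- N = 50: k = 0 gives 17/50 = 34%; k = 1 gives 16/50 = 32%; k = 2 gives 15/50 = 30%.
- N = 200, same k: 68/200 = 34%; 67/200 = 33.5%; 66/200 = 33%.

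**5. Scale against sampling error.** At 17/50 the 95% half-width is 1.96 × √(0.34 × 0.66 / 50) = 13.1 points. A shift of 2 to 4 points lies well inside that. It is a one-directional misclassification, however, and the interval does not reflect it.

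**The case against.** The strongest reply is that the obligation to obtain the mRS already exists. Section 5.8.1 says the day-180 measures will be assessed and allows phone or mail, the schedule of events lists an mRS at six months, and 7.3 asks for every effort. Section 8.1 deals with why an appointment was missed and does not waive any of this. The window is ±28 days, so an event at day 175 still leaves until day 208 for a call. Deaths are scored 6, so the worst deteriorations are counted. This stands, and it limits the point. A reader might infer that 8.1 restricts the contact to learning the reason; the text does not say so. What remains is that 8.1 does not connect the contact to the 5.8.1 assessment, and 7.3 does not say that an mRS obtained that way prevents carry-forward.

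A reader might also infer that most missing outcomes are SAE-driven and that the primary rate is therefore known to be inflated. The documents do not support this. Section 7.3 attributes missing data mainly to loss to follow-up, which section 8 defines by repeated failed contact. Those subjects are not the ones the site has reached. A missed 30- or 90-day visit has no effect on the primary endpoint if the 180-day mRS is obtained. An SAE such as a re-hospitalization need not change the mRS.

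The registry is descriptive, with no hypothesis test planned. That lowers the consequence, but the mRS 0-3 proportion is still the primary clinical result.

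Finally, 7.3 leaves further detail to a statistical analysis plan, so an analysis could be added there. The conclusion is therefore restricted to analyses stated in this document. A later plan cannot, however, recover an mRS that the site never collected.

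**Conclusion.** The point holds as a limited gap in data collection and missing-data handling. As written, 7.3 can score a survivor with a recorded later deterioration as favorable, and no analysis stated in the document can score that subject as unfavorable.

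It applies only to survivors with no 180-day mRS, a last mRS of 0-3 and a true decline beyond 3. For those subjects the error can only raise the rate, by 2 points each at 50 subjects or 0.5 point each at 200. Their number is not given and may be zero. The illustrative 34% to 30% rests on assuming 0 to 2 such subjects of 50.

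The documents do not establish that the primary rate will be biased upward overall. Nor do they support scoring every SAE-related miss as a failure in the primary analysis, which would misclassify subjects whose event left no lasting disability.

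**What to change.** Three changes:

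1. **8.1:** require that the contact for a missed visit also obtains vital status and an mRS, by a mode that 5.8.1 permits, and records the date of each. If the mRS falls in the visit window, use it as that visit's mRS.
2. **7.3:** apply carry-forward only when no mRS was obtained within the window by any permitted mode.
3. **7.3:** add a sensitivity analysis that counts survivors with no 180-day mRS and an SAE after their last mRS as not mRS 0-3, and report how many there are. Leave the primary analysis without this rule.

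The cost is a few minutes on a call the site should already be making, one more analysis, and possibly a slightly less favorable reported rate. The 8.1 change is useful only while follow-up is still under way, so it should not wait for the statistical analysis plan.
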